2.13.2 Magnetic resonance imaging

2.13.2.1 Objectives

To examine the changes in cardiac structure, function, and fibrosis after 8 months of treatment with sacubitril/valsartan or enalapril.

2.13.2.2 Endpoints

All baseline and 8-month MRI measurements are described in the Manual of Cardiovascular Magnetic Resonance Imaging Substudy, categorized into assessments of left ventricular (LV), right ventricular (RV), left atrium (LA), right atrium (RA), myocardial edema of LV, myocardial delayed enhancement – myocardial fibrosis, T1 mapping, T2 mapping, and clinical and laboratory data peri-MR.

2.13.2.3 Statistical hypothesis, model, and method of analysis

Summary statistics by treatment arm will be presented for each MRI measurement. Evaluations of all MRI measurement at 8-month will be performed adjusted for baseline values. The reduction of fibrosis and the improvement of cardiac structure after 8 months of treatment will be analyzed using generalized mixed linear models considering the hierarchical effect of study site and participant. Results will be graphically displayed in boxplots. Missing values will not be imputed; analyses will be performed on FAS populations, including only participants with available MRI data.

3 Change to protocol specified analyses

SAP second version includes the recurrent event as a key secondary endpoint, changed the number of days alive out of the hospital time definition changed to within 1 year from randomization, and the NT-ProBNP evaluation at month 8 was included as exploratory endpoint.

4 Appendix

4.1 PARACHUTE-HF Win Ratio bootstrap algorithm

1. The **win_ratio()** function determines the winner in each match between Enalapril and Sacubitril/Valsartan patients based on a hierarchical evaluation. The **win_ratio** function will be used in the pairs of patients from both groups within each stratum.
 - If the Sacubitril patient dies, and their follow-up time is shorter (regardless of whether the other patient dies), Enalapril wins. Conversely, if the Enalapril patient dies and their follow-up time is shorter, Sacubitril wins. Otherwise, it is a tie.
 - If the participants tied using previous comparison then a comparison in time to first HF hospitalization is performed: if the Sacubitril patient is hospitalized for heart failure (HF) and the time to first hospitalization is shorter than that of the Enalapril patient (or shorter than their total follow-up time if they were hospitalized for HF), Enalapril wins. The same logic applies in reverse for Sacubitril. Otherwise, it is a tie.
 - If the participants tied using previous comparison then a comparison in NT-ProBNP changes within 12 weeks is performed: The **NT_ProBNP_relative_change** endpoint is defined as the ratio: **NT-ProBNP at Week 12 / NT-ProBNP at Baseline**. The match outcome is determined as follows:
 - If $\text{NT_ProBNP_change_Sacubitril} < 0.75 \times \text{NT_ProBNP_change_Enalapril}$, Sacubitril wins.
 - If $\text{NT_ProBNP_change_Enalapril} < 0.75 \times \text{NT_ProBNP_change_Sacubitril}$, Enalapril wins.
 - Otherwise, it is a tie.
2. **Matrix W** contains the weight assigned to each country, calculated as $1/N_i$, where N_i represents the number of patients per stratum i , with i belonging to {Argentina, Brazil, Colombia, Mexico}.
3. **resultados_wr(BR)** is a data frame containing match results for Sacubitril vs. Enalapril patients in **Brazil**, computed using the **win_ratio()** function. Similar datasets (**resultados_wr(AR)**, **resultados_wr(CO)**, **resultados_wr(MX)**) are created for the remaining strata.
4. **resultados_wr** compiles all match results into a single data frame.

5. Calculates the total number of wins for each group and the number of ties per stratum and overall. In each stratum, the observed **Win Ratio (WR)** is calculated as the number of Sacubitril wins divided by the number of Enalapril wins.
6. The **Dong's Win Ratio** is then computed using the weights from **W** and the number of wins in each stratum:

$$\psi = \frac{\sum_{i=1}^4 w^{(i)} n_{Sacubitril}^{(i)}}{\sum_{i=1}^4 w^{(i)} n_{Enalapril}^{(i)}}$$

To compute the bootstrap:

1. **Resampling:** Perform resampling of the patients with replacement, maintaining the original number of patients per group in each stratum **M** times. ($M \geq 10,000$)
2. **Match Evaluation:** For each resampled stratum, compute match outcomes using **resultados_wr**.
3. **Win Ratio Computation:** Calculate the Win Ratio **M** times for each country.
4. **Dong's Win Ratio Estimation:** Compute the Dong's Win Ratio for all **M** samples using matrix **W** (since stratum sizes remain unchanged), storing results in an auxiliary variable **Strata_results**.
5. **Confidence Interval Calculation:** Compute and return the **95% confidence interval (CI)** for each stratum and the overall Dong's Win Ratio using the **2.5th and 97.5th percentiles** of the **M** resamples.

5 Reference

Bocchi, E. A., Rassi, S., & Guimarães, G. V. (2018). Safety profile and efficacy of ivabradine in heart failure due to Chagas heart disease: a post hoc analysis of the SHIFT trial. *ESC Heart Failure*, 5(3), 249–256. <https://doi.org/10.1002/ehf2.12240>

D. Y. Lin, L. J. Wei, I. Yang, & Z. Ying. (2000). Semiparametric Regression for the Mean and Rate Functions of Recurrent Events. *Journal of the Royal Statistical Society. Series B (Statistical Methodology)*, 62(4), 711–730. <http://www.jstor.org/stable/2680616>

de Diego, C., González-Torres, L., Núñez, J. M., Centurión Inda, R., Martín-Langerwerf, D. A., Sangio, A. D., Chochowski, P., Casasnovas, P., Blazquez, J. C., & Almendral, J. (2018). Effects of angiotensin-neprilysin inhibition compared to angiotensin inhibition on ventricular arrhythmias in reduced ejection fraction patients under continuous remote monitoring of implantable defibrillator devices. *Heart Rhythm*, 15(3), 395–402. <https://doi.org/10.1016/j.hrthm.2017.11.012>

Grambsch P, Therneau T (1994), Proportional hazards tests and diagnostics based on weighted residuals. *Biometrika*, 81: 515-26.

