1.1 Study design

This is a Phase 4, multinational, multicenter, parallel-group, prospective, randomized, open-label, blinded-endpoint adjudication (PROBE), active-controlled study has been designed to evaluate the effect of sacubitril/valsartan over enalapril in CCC population. The study is aiming to validate the hypothesis that Sacubitril/Valsartan is superior as compared to Enalapril in improving a composite of Time to CV events (CV death or first HF hospitalization) or in causing a greater reduction or lesser increase in NT-proBNP levels at Week 12 in participants with HFrEF caused by CCC. The study will consist of a Screening Epoch, and a Randomized Treatment Epoch consisting of a Titration Period, and a Follow-up Periods shown in Figure 1.

The target projected sample size is 900 participants (450 in each arm). It is estimated that approximately 1800 participants will be screened at up to approximately 100 study sites due to an anticipated 50% screen failure rate, based on previous HF study experiences.

Figure 1. Study design

Upon signing the informed consent form, each subject is uniquely identified by the academic research organization (ARO) to the study site by interactive web response system (IWRS). Once assigned to a subject, the identification will not be reused. If the subject fails to be randomized for any reason, the IWRS must be notified within 2 days that the subject was not randomized. The reason for not being randomized will be entered on Screening phase disposition electronic Case Report Form (eCRF).

After confirming that the subject fulfills all the inclusion/exclusion criteria, the Investigator or his/her delegate will log in to IWRS to randomize the subject to one of the treatment arms. The subject identification will be used to link the subject to a treatment arm and will specify a unique medication number for the first package of study treatment to be dispensed to the subject.

The primary endpoint is the hierarchically ordered composite endpoint consisting of time to CV death, time to first heart failure hospitalization (HFH) within 36 months follow-up and the relative change from baseline to Week 12 in NT-ProBNP.

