2.5 Analysis of the primary objective

2.5.1 Primary Endpoint

The primary endpoint is the hierarchically ordered composite endpoint consisting of time to CV death (worst category; earlier time to CV death is unfavorable), time to first Hospitalization due to Heart Failure (second worst category; earlier time to Hospitalization due to HF is unfavorable) and the relative change from baseline to Week 12 in NT-ProBNP (best category; more reduction or less increase are favorable) (Table 1). CV events will be confirmed by an independent Clinical Endpoint Adjudication Committee (CEC).

The effect is measured through the unmatched win ratio. The win ratio is based on pair-wise comparisons between participants receiving sacubitril/valsartan and participants receiving enalapril. A winner in the pair-wise comparison has a delayed time to the occurrence of CV death; if time to the occurrence of CV death is censored, a winner has a delayed time to the occurrence of first HF hospitalization event; if the times to both cardiovascular events are censored, winner has a smaller change (more

reduction or less increase) in NT-proBNP between baseline and Week 12. The FAS will be used for the primary analysis.

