2.5.2 Statistical hypothesis, model, and method of analysis

The following primary analysis will be tested as (Wang and Pocock, 2016):
H0: $\Psi \leq 1$ (win ratio ≤ 1) - The true number of 'winners' for sacubitril/valsartan is less than or equal to the true number of winners for enalapril.

H1: $\Psi > 1$ (win ratio > 1) - The true number of 'winners' for sacubitril/valsartan is larger than the true number of winners for enalapril.

The primary efficacy endpoint will be analyzed using the win ratio approach (Pocock et al 2012), with treatment as fixed-effect factor and stratified by country (Dong et al. 2017). Every patient in the sacubitril/valsartan arm will be compared to every patient in the enalapril arm within each stratum (country). All pairs will be compared first by time to CV death; if there is no winner, they will be compared for time to first HF hospitalization; if again there is no winner, they will be compared according to reduction in NT-proBNP levels between randomization and Week 12. If the comparison between changes in NT-proBNP levels does not result in a winner, the respective pairwise comparison is tied. When comparing the time to an event between two participants and at least one of the times is censored, the comparison is only performed up to the censoring time. The comparison of NT-proBNP is performed based on the relative change between randomization and Week 12 and takes into account that relative changes within $\pm 25\%$ are considered medically irrelevant; in detail, let x_{LCZ696} and x_{Enal} be the relative changes of participants in the sacubitril/valsartan and the enalapril arm, respectively. Then, a comparison of NT-proBNP is in favor of the subject in the sacubitril/valsartan arm if $x_{LCZ696} < 0.75 x_{Enal}$. On the other hand, the comparison is in favor of the subject in the enalapril arm if $x_{Enal} < 0.75 x_{LCZ696}$.

The win ratio is estimated by the ratio of the number of winners in the sacubitril/valsartan group and the number of winners in the enalapril group with weights defined as the reciprocal of the stratum (country) sample size.

$$\Psi = \frac{\sum_m^M w^{(m)} n_{LCZ696}^{(m)}}{\sum_m^M w^{(m)} n_{Enal}^{(m)}}$$

Where $n_{LCZ696}^{(m)}$ and $n_{Enal}^{(m)}$ are the total number of wins in the m^{th} stratum for the sacubitril/valsartan and Enalapril groups, respectively; $w^{(m)} = 1/N^{(m)}$ and $N^{(m)}$ is the total sample size in the m^{th} stratum.

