2.11 Sample size calculation

An analysis of the 55 patients with Chagas' disease in the enalapril group in PARADIGM (Ramires et al 2018) showed an event rate of 20 events per 100 subject-years for CV death plus hospitalization due to HF. Similar event rates, for CV death plus hospitalization due to HF in CCC patients, has also been seen in the BENEFIT and SHIFT studies. Therefore, we assumed a rate of approximately 20 events per 100 subject-years for the CV event (composite of CV death and first HF hospitalization) for the enalapril group. Approximately 66% of the first CV events are HF hospitalizations. For the sample size calculation, we assumed a rate of 16 events per 100 subject-years for the sacubitril/valsartan group, which corresponds to an effect of 20%.

The sample size was determined based on a simulation study under the assumptions of:

- a one-sided type I error rate of 2.5%,
- a target power of 85%,
- a uniform accrual of 18 months,
- a study duration of 36 months, i.e. the individual follow-up times varied between 18 and 36 months,
- an annualized event rate of 0.16 for the composite of CV death or first HF hospitalization in the sacubitril/valsartan group, and an annualized event rate of 0.20 for the composite of CV death or first HF hospitalization in the enalapril group,
- a relative change of NT-proBNP between week 12 and baseline that is 25% lower in the sacubitril/valsartan group compared to the enalapril group

During the simulation study, a simulated trial was considered to show superiority of sacubitril/valsartan over enalapril when the win ratio was significantly larger than one based on the one-sided significance level of 2.5%, and the estimated hazard ratio of sacubitril/valsartan versus enalapril for time to first HF hospitalization was less than one, and the estimated hazard ratio of sacubitril/valsartan versus enalapril for CV death was less than one.

Based on these assumptions and criteria for superiority, a study with 900 patients results in the target power of 85%. Moreover, 302 participants with events for the composite of CV death or first HF hospitalization can be expected in the study.

As the primary hierarchical composite endpoint is evaluable as long as subject experience either a HF hospitalization, CV death, or have a NT-proBNP value measured at Week 12, the sample size calculation did not assume any loss of follow-up.

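### SAP Appendix 4.1: the pairwise win-ratio rules contradict SAP 2.5.1 to 2.5.2.2 on heart-failure hospitalisation, and do not limit death to CV death

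*SAP*

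**What the plan says.** SAP 2.5.1 and 2.5.2 set the hierarchy as CV death, then first HFH, then NT-proBNP. On moving from the first tier to the second, 2.5.1 says: "if time to the occurrence of CV death is censored, a winner has a delayed time to the occurrence of first HF hospitalization event". On censoring, 2.5.2 says that when "at least one of the times is censored, the comparison is only performed up to the censoring time". Section 2.5.2.1 censors time to CV death at a non-CV death. Section 2.5.2.2 gives every participant without an HFH a censoring date (death, withdrawal of consent or last visit). The primary estimand (2.5.1.1 and Table 5) uses only data before a non-CV death.

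Section 2.5.2 allows the analysis to be run in R code or with the WINS package, and points to Appendix 4.1 for the bootstrap algorithm. The appendix spells out the function that decides each pair. Its first tier reads: "If the Sacubitril patient dies, and their follow-up time is shorter (regardless of whether the other patient dies), Enalapril wins", with the converse for the other arm. In its second tier, a hospitalised sacubitril/valsartan participant loses if the HFH time is shorter than the enalapril participant's, with the bracketed alternative "or shorter than their total follow-up time if they were hospitalized for HF), Enalapril wins". The same logic is reversed for the other arm, and every other pair is a tie that passes to NT-proBNP.

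**The concern.** Appendix 4.1 is the only step-by-step description of how a pair is decided, and the same function feeds both the point estimate and every bootstrap resample. A programmer or independent validator would naturally code from it. Two of its conditions differ from the method section.

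- **HFH tier.** The follow-up comparator is attached to the wrong group, namely participants who were hospitalised.
- **Death tier.** The trigger is a death of unstated cause, although the endpoint is CV death and a non-CV death is a censoring event.

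At stake is a primary estimate and confidence interval that could depend on the order of statements in a program, or on deaths that the primary estimand does not count.

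**Working it through.** **Inputs from the documents.** SAP 1.1: "The target projected sample size is 900 participants (450 in each arm"). SAP 2.11: "an annualized event rate of 0.16 for the composite of CV death or first HF hospitalization in the sacubitril/valsartan group", and 0.20 in the enalapril group; about 66% of first events are HFH; uniform accrual over 18 months; follow-up of 18 to 36 months; a Week 12/baseline NT-proBNP ratio 25% lower on sacubitril/valsartan; no loss to follow-up.

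**Assumptions not in the documents.** SD of the log NT-proBNP ratio 0.8 (0.5 to 1.1 for the power check); non-CV death 0.005 to 0.05 per year; a hazard of CV death after HFH of 1 to 4 times that before it. Simulations are unstratified.

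**1. The plan's own figures.** With follow-up uniform on 1.5 to 3 years, expected events per arm are 450 × [1 − (e^(−1.5r) − e^(−3r))/(1.5r)].

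- r = 0.20: 450 × [1 − (0.7408 − 0.5488)/0.30] = 162.0
- r = 0.16: 450 × [1 − (0.7866 − 0.6188)/0.24] = 135.3

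The total is 297.3 against the stated 302, a gap of 1.6%. Simulated power under the plan's success rule is 0.82 to 0.88 over log-SD 0.5 to 1.1, which brackets 85%. The model therefore represents the design.

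**2. What the bracket does when both were hospitalised.** Let h be the HFH time and F total follow-up, with subscripts S (sacubitril/valsartan) and E (enalapril). As written, enalapril wins if h_S < h_E or h_S < F_E, and sacubitril/valsartan wins if h_E < h_S or h_E < F_S. Because h_E < F_E, the second clause contains the first, so the comparison of the two hospitalisation times no longer matters. Both arms win whenever h_S < F_E and h_E < F_S, that is, unless one HFH falls after the other participant's follow-up has ended. In simulation about 82% of both-hospitalised pairs that reach this tier meet both conditions.

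**3. Effect of coding order under a true null.** Shares of all pairs, in the order death + HFH + NT-proBNP (400 trials, log-SD 0.8, non-CV death 0.03 per year, doubled hazard after HFH). The second row also codes any death and gives non-hospitalised participants no HFH time; under the null neither change favours an arm.

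| Rule | Sacubitril/valsartan wins (%) | Enalapril wins (%) | Win ratio |
|---|---|---|---|
| SAP 2.5.2 | 12.3 + 13.6 + 18.7 = 44.6 | 12.4 + 13.6 + 18.7 = 44.7 | 1.00 |
| Bracket coded literally, enalapril-wins condition tested first | 17.2 + 0.3 + 24.7 = 42.2 | 17.2 + 3.5 + 24.7 = 45.4 | 0.93 |

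Reversing the order swaps the columns: 45.4/42.2 = 1.08. At non-CV death 0.02 per year, across both readings in step 4, the null win ratio is about 0.91–0.93 in one order and 1.08–1.10 in the other. In the order tabulated, none of the 400 null trials was significant. The error rate in the opposite order was not estimated.

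**4. Pairs with one hospitalised participant.** The result depends on what a non-hospitalised participant's HFH time is taken to be.

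- *No value:* the first clause has no comparator and the bracket does not apply. The pair ties and passes to NT-proBNP. HFH-decided pairs fall from about 28% to 4%.
- *The 2.5.2.2 censoring date:* the first clause decides the pair, and HFH still decides about 28%.

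**5. Death tier coded as any death.** Win ratio at planning effects, with the HFH tier coded correctly. Ranges are from separate simulation runs.

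| Assumed non-CV death rate per year | CV death only | Any death |
|---|---|---|
| 0.01 | 1.40–1.41 | 1.39 |
| 0.02 | 1.42 | 1.37 |
| 0.03 | 1.41 | 1.35 |
| 0.05 | 1.42–1.43 | 1.32–1.33 |

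At 0.005 the difference is within simulation noise. At 0.03, pairs decided by death rise from 12.4 + 9.8 = 22.2% to 17.4 + 14.8 = 32.2%.

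**The case against.** The best defence is that the method section is clear and should govern. It fixes CV death as the first tier, censors non-CV death and compares only up to the censoring time. On that view the bracket has simply lost a *not*, since a rule that lets both arms win the same pair cannot be intended, and the appendix's verb for death is shorthand for CV death. Section 2.5.2.1 also counts all undetermined deaths as CV, so only deaths adjudicated as non-CV could be affected. The analysis may be run in the WINS package without using these sentences.

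Most of this stands, and it limits the point to a contradiction within the SAP. It also removes two stronger inferences.

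- A reader might infer that the HFH tier collapses into the biomarker tier. That follows only if non-hospitalised participants are given no HFH time, and 2.5.2.2 supplies one.
- A reader might infer that the appendix text is really the supplementary all-cause estimand. It is not: that estimand also censors at treatment crossover (2.5.1.2 and Table 6), and the appendix has no such step.

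The order dependence is not removed. It arises under either reading of the HFH time for as long as the bracket is coded as written.

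**Conclusion.** The point holds as a contradiction between Appendix 4.1 and the primary-endpoint definition. Its two parts differ in strength.

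The HFH bracket is a plain textual error. Coded literally, it biases the win ratio by roughly 7 to 10% in a direction set by coding order. The overlap that causes this was 80 to 83% of both-hospitalised pairs in every setting run. The exact size rests on the assumed log-SD, non-CV death rate and hazard after HFH.

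The death wording is imprecise and not clearly wrong. If coded as any death it would depart from the primary estimand, with an effect that runs from negligible to about 0.1 on the win ratio over the assumed rates.

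A reader might go further and conclude that the trial has changed its primary endpoint to all-cause death, or that the reported analysis will be wrong. The documents support neither: 2.5.1 to 2.5.2.2 state the intended endpoint, and the final program is not shown. It is still worth correcting before the analysis, because the faulty text describes the function behind the primary result and its interval.

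**What to change.** Change two sentences in Appendix 4.1, each with its mirror image for the other arm:

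- **Death tier:** *If the sacubitril/valsartan participant has a CV death (as defined in 2.5.2.1) and the time to it is shorter than the enalapril participant's time to CV death or censoring, enalapril wins.*
- **HFH tier:** *If the sacubitril/valsartan participant is hospitalised for HF and the time to first HFH is shorter than that of the enalapril participant, or shorter than the enalapril participant's HFH censoring time (2.5.2.2) if that participant was NOT hospitalised for HF, enalapril wins.*

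State the supplementary version separately, with all-cause death and censoring at treatment crossover as in 2.5.1.2 and Table 6. Then check the program against 2.5.2 on hand-worked pairs: both hospitalised; one hospitalised before the other's censoring; one hospitalised after it; a non-CV death first; and a CV death in one arm. As a further test, swapping the arm labels must invert the win ratio exactly; a program that depends on coding order will fail.

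The cost is two sentences, a short supplementary paragraph and a program check. No data collection or sample size changes.
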